10.3.2.2 Efficacy Analyses

Endpoint	Statistical Analysis Methods to Support Estimands
Primary	Bayesian Hierarchical Model will be used to evaluate primary efficacy estimand.
Secondary	Bayesian Hierarchical Model/Generalized linear model will be used to evaluate secondary efficacy endpoints. Details will be described in the SAP.
Exploratory	Details of the analysis of exploratory endpoints will be specified in the SAP.

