3.1 Study Design

This is a Bayesian adaptive phase 2b, multi-center, double-blind, randomized, placebo controlled, 52-week, dose-ranging study in subjects with active SLE and inadequate response to SOC therapies including OCS, immunosuppressants, and immunomodulators. Subjects will be randomized to receive either placebo or 1 of 3 doses of rozibafusp alfa with the last dose at week 50. Study duration for a single subject will be 52 weeks plus the screening period and safety follow-up period.

Treatment will be administered every 2 weeks (Q2W). Subjects are required to attend as many follow-up visits as necessary to ensure a minimum of 16 weeks of safety follow-up after the last administration of the investigational product. Tapering of OCS from the baseline dose will be allowed from week 24 through week 44. The first interim analysis (IA) will be executed after the first 40 enrolled subjects have had the opportunity to complete the week 24 assessment. Additional IAs may be executed after approximately every 32 newly enrolled subjects have had the opportunity to complete the week 24 assessment. The last IA will occur when all 320 subjects are randomized and have had the opportunity to complete the week 24 assessment. This IA will be referred to as the 'all-subjects-week-24 IA'. The purpose and analyses planned at each IA are listed in [Table 3-1](#).

Based on the Data Monitoring Committee's recommendation following review of the results from the 6th IA and subsequent decision by the Data Access Plan Team, the study was terminated due to futility and further enrollment in the study was stopped. Previously enrolled subjects were discontinued from IP and terminated the study after being followed for an additional 16 weeks following last dose of IP. The remaining planned IAs, including the last IA ('all-subjects-week-24-IA') and the primary analysis, were not conducted.

Table 3-1. Planned Analyses Schedule: Decisions at each Interim Analysis, Primary Analysis, and Final Analysis

Time point	Adaptive Decision	Number of subjects with opportunity to complete week 24
1 st IA	RAR	40
2 nd IA	Futility, RAR	72
3 rd IA	Futility, RAR	104

4 th IA	Futility, RAR	136
5 th IA	Futility, RAR	168
6 th IA	Futility, RAR	200
7 th IA ^{ac}	Futility, RAR	232
Last IA ^{bc}	Administrative Success	320
Primary Analysis ^c	Not applicable	All subjects have had the opportunity to complete week 52
Final Analysis	Not applicable	All subjects reach EOS

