5.1 Basic Definition

Investigational Product (IP)

Rozibafusp alfa and placebo.

Enrollment/Randomization Date

The enrollment/randomization date is the date on which a subject is assigned to a treatment group.

First Dose Date

The first dose date is the date of administration of the first dose of IP; this may or may not be the same as randomization date.

Actual Treatment Received

The actual treatment received is the IP the subject actually received, regardless of what the subject was randomized to. In cases where a subject received both rozibafusp alfa and placebo, the actual treatment received will be the rozibafusp alfa dose. In cases where a subject received multiple rozibafusp alfa doses, the actual treatment received will be based on the highest rozibafusp alfa dose received.

Duration of IP exposure

The duration of IP exposure will be derived as the date of the last IP administration plus 13 days (14-day window - 1), end of study or cutoff date, whichever occurs first, minus the date of first IP administration plus 1 day.

Flare Exposure Time

The flare exposure time is the time from study day 1 up to the last flare assessment date.

Treatment-emergent adverse event

Treatment emergent adverse events are defined as events categorized as Adverse Events (AEs) starting on or after first dose of IP as determined by "Did event start before first dose of investigational product?" equal to "No" or missing on the Events eCRF and up to the end of study date.

Baseline medication

Baseline medication is defined as any medication with start date on or before study day 1 and ongoing while on study.

Concomitant medication

Concomitant medication is defined as any medication with start date prior to the study day 1 and ongoing while on study or any medication with start date on or after study day 1 and up to the end of study.

Prednisone-equivalent dose

Prednisone-equivalent dose will be computed based on the table below. Additionally, a multiplier will be applied depending on the dosing frequency: 2 for 'twice daily' or 'every

12 hours' and 0.5 for every other day. For example, cortisone 25 mg is equivalent to prednisone 5 mg and a cortisone 25 mg twice daily is equivalent to prednisone 10 mg/day.

Corticosteroid	Equivalent daily dose
Prednisone	5 mg
Betamethasone	0.75 mg
Cortisone	25 mg
Deflazacort	6 mg
Dexamethasone	0.75 mg
Hydrocortisone	20 mg
Methylprednisolone/Meprednisone/Methylprednisolone Acetate	4 mg
Prednisolone	5 mg
Triamcinolone	4 mg

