5.2 Study Points of Reference

Baseline

Baseline is defined as the closest recorded measurements prior to or on the first dose of study treatment for subjects receiving study treatment regardless of time collected. For subjects not receiving treatment, baseline is defined as the closest recorded measurements prior to or on the enrollment date.

Study Day 1

Study day 1 for each subject is the first day of IP administration or the day of randomization for subjects who did not receive IP.

Study Day

Study day for each subject is defined as (day of interest – study day 1) + 1 for dates on or after study day 1, or (day of interest – study day 1) for dates prior to study day 1.

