To distinguish between mild and moderate flare an additional question, “Status”, was added to the classic instrument. Based on the investigator’s clinical judgement, the flare is to be classified as one of the following 4 options: No Flare,

[figure not shown]
Mild Flare, Moderate Flare, Severe Flare. SELENA-SLEDAI flare data collected in ClinicalLink were transcribed to Rave and hence will be excluded from analyses to avoid duplicate records.

Annualized Flare Rate

The annualized flare rate will be calculated as the number of flares divided by the flare exposure time in days multiplied by 365.25.

Systemic Lupus International Collaborating Clinics/American College of Rheumatology Damage Index (SDI)

The SDI global score will be calculated as the sum of the damage scores (0-47) from 12 organ systems with the following possible scores: ocular (0-2), neuropsychiatric (0-6), renal (0-3), pulmonary (0-5), cardiovascular (0-6), peripheral vascular (0-5), gastrointestinal (0-6), musculoskeletal (0-7), skin (0-3), premature gonadal failure (0-1), diabetes (0-1) and malignancy (0-2).

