8.3 Handling of Missing and Incomplete Data

Subjects may have missing specific data points for a variety of reasons. In general, data may be missing due to a subject's early withdrawal from study, a missed visit, or non-evaluability of a specific clinical or laboratory measurement at its planned clinical visit.

Additionally, as the study was terminated before the planned completion, subjects may have missed clinical visits including not completing the week 52 visit. For efficacy and PRO outcomes, subjects who terminated early due to sponsor decision will be excluded from analyses of data from visits for which they did not have the opportunity to participate in by the date of study termination decision being communicated to sites, i.e. February 28, 2023. Efficacy data collected after this date will be censored and excluded from analyses for that particular visit.

Unless specified, no imputation will be used. The general procedures outlined below describe what will be done when a data point is missing.

Hybrid SLEDAI

In case of completely missing hSLEDAI assessment (e.g. missed visit) or partially missing (e.g. laboratory measurements not available), the missing post-baseline hSLEDAI items will be imputed using last observation carried forward (LOCF) if the previous analysis visit is not missing. Baseline hSLEDAI will not be carried forward to post-baseline.

The hSLEDAI total score will then be computed based on the non-missing and imputed data. **If the hSLEDAI total score cannot be evaluated after imputation, the hSLEDAI score \geq 4 points reduction from baseline will be considered not met.**

CLASI

In case of completely missing CLASI assessment (e.g. missed visit) or partially missing, the missing post-baseline CLASI items will be imputed using LOCF if the previous analysis visit is not missing. Baseline CLASI will not be carried forward to post-baseline.

The CLASI activity score will then be computed based on the non-missing and imputed data. If the CLASI activity score cannot be evaluated after imputation, the CLASI activity score \geq 50% improvement endpoint will be considered not met.

BILAG

In case of completely missing BILAG assessment (e.g. missed visit), the missing post baseline BILAG item scores will be imputed using LOCF if the previous analysis visit is not missing.

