9.1 General Considerations

All categorical variables will be summarized using the number and percent of subjects falling into each category and all continuous variables will be summarized using mean,

standard error (SE) or standard deviation (SD), median, first quartile (Q1), third quartile (Q3), minimum, maximum, and number of subjects with observations. Safety endpoints will be summarized descriptively, including the treatment-emergent adverse events and serious adverse events, clinically significant changes in laboratory values and vital signs, and incidence of [REDACTED]. All safety analyses will be performed using the Safety Analysis Set based on subject's actual treatment received.

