
 • Annualized moderate and severe flare rate (as measured by SELENA-SLEDAI Flare Index) over 52 weeks • Annualized severe flare rate (as measured by SELENA-SLEDAI Flare Index) over 52 weeks • Annualized flare rate (as measured by BILAG score designation of “worse” or “new” resulting in a B score in ≥ 2 organs or an A score in ≥ 1 organ) over 52 weeks 	Descriptive statistics will be summarized by randomized treatment arm.

 • Total tender and swollen joint count (limited to hands and wrists) $\geq 50\%$ improvement from baseline at week 12, 24, 36, and 52 in subjects with ≥ 6 tender and swollen joints involving the hands and wrists at baseline • CLASI activity score $\geq 50\%$ improvement from baseline at week 12, 24, 36, and 52 in subjects with a CLASI activity score ≥ 8 at baseline 	Number and percentage of subjects achieving response of interest will be summarized by randomized treatment arm.

• PROMIS-Fatigue score and change from baseline at week 12, 24, 36, 44, and 52• SF36v2 score and change from baseline at week 12, 24, 36, 44, and 52• LupusQoL score and change from baseline at week 12, 24, 36, 44, and 52• PtGA score and change from baseline at week 12, 24, 36, 44, and 52	Descriptive statistics will be summarized by randomized treatment arm.
---	---

Table 9-3. Exploratory Efficacy Endpoints Summary Table

Endpoint	Primary Summary and Analysis Method
REDACTED	REDACTED

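### After early termination, the three annualized flare rates need a rate per person-year in each arm; unweighted statistics of subject-level rates are a noisy summary

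*SAP*

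**What the plan says.** SAP section 5.6 gives the formula: "The annualized flare rate will be calculated as the number of flares divided by the flare exposure time in days multiplied by 365.25". Section 5.1 fixes the denominator: "The flare exposure time is the time from study day 1 up to the last flare assessment date". Section 5.2 sets its starting point subject by subject: "Study day 1 for each subject is the first day of IP administration".

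Table 9-2 covers three flare endpoints: SELENA-SLEDAI moderate and severe, SELENA-SLEDAI severe, and BILAG. The whole analysis entry for them is "Descriptive statistics will be summarized by randomized treatment arm". Section 9.1 explains what that means: "all continuous variables will be summarized using mean", with SE or SD, median, quartiles, minimum, maximum and n. These statistics need one value per subject, so the natural reading is an unweighted summary of subject-level rates. The SAP does not say so in as many words.

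On follow-up, section 3.1 reports that "the study was terminated due to futility and further enrollment in the study was stopped" after the sixth interim analysis. Section 8.3 sets the cut at 28 February 2023: "Efficacy data collected after this date will be censored and excluded from analyses for that particular visit".

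The SAP states no minimum exposure, pooled person-time rate, exposure weighting or count model with an exposure offset. Section 10 replaces all treatment comparisons by descriptive statistics.

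**The concern.** An annualized rate from a short follow-up is mostly multiplier. If all subjects were followed for about 52 weeks, the mean of subject rates and the rate per person-year would nearly coincide, and the choice would not matter. This trial stopped early, so an endpoint labelled as over 52 weeks will rest on follow-up of very different lengths. A subject seen once after baseline then has the same influence on the arm mean as a subject followed for a year, and one flare in the former produces an extreme value.

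Since comparisons have been removed, the descriptive values are all that will be reported for three secondary endpoints. A reader will compare arm means, and a few short follow-ups could move them.

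**Working it through.** **Plan's own figure.** The documents give no expected flare rate, event count or precision for these endpoints, so there is nothing to reproduce. The 320 subjects and 80% power concern SRI-4.

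**Inputs from the documents.** The rate formula (SAP 5.6), the exposure definition (5.1), and the target days of the efficacy visits (Appendix D): week 4 is day 29, then every 28 days to day 365. The number of subjects cut short, when they were cut, and the true flare rates are not given. They are assumed below and shown as ranges.

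**Step 1: one flare under the SAP formula**, 1 / days × 365.25:

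| Last flare assessment | Rate per year |
|---|---|
| day 29 | 12.59 |
| day 57 | 6.41 |
| day 85 | 4.30 |
| day 169 | 2.16 |
| day 365 | 1.00 |

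**Step 2: a small example.** Nine subjects are followed for 365 days with five flares among them (one each in five subjects), and a tenth is cut at day 29 with one flare.
- Mean of subject rates: (5 × 1.0007 + 12.595) / 10 = 1.76 per year.
- Rate per person-year: 6 / (9 × 365 + 29) × 365.25 = 6 / 3314 × 365.25 = 0.66 per year.

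**Step 3: precision when truncation is unrelated to flaring.** With Poisson flares at a common rate, both summaries are unbiased. The variance of the mean of rates is proportional to mean(1/T), and that of the pooled rate to 1/mean(T). The variance ratio is therefore mean(T) × mean(1/T), whatever the flare rate. Suppose cut subjects end at a monthly visit from day 29 to day 337 with equal chance (mean T = 183 days, mean 1/T = 0.009074), and the rest reach day 365:
- 10% cut: 346.8 × 0.003373 = 1.17
- 25% cut: 319.5 × 0.004323 = 1.38
- 40% cut: 292.2 × 0.005273 = 1.54
- 70% cut: 237.6 × 0.007174 = 1.70

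Simulation with 60 per arm and 0.2 to 1.0 flares per year agrees: 1.15 to 1.18, 1.37 to 1.38 and 1.53 to 1.56 for 10%, 25% and 40% cut, with both summaries centred on the true rate. When subjects differ in underlying flare risk (gamma frailty), the ratio moves towards 1. With frailty variance 0.5 to 2 and 10 to 40% cut, it was 1.04 to 1.37. Across plausible settings, about 1.1 to 1.7 is fair.

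If cuts occur only from week 24 (days 169 to 337, mean T = 253, mean 1/T = 0.004165), the ratio is 337.0 × 0.003096 = 1.04 at 25% cut and 286.6 × 0.003737 = 1.07 at 70%, so about 1.05.

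In the same simulation at 25% cut from week 4, the chance that at least one subject in an arm shows 6 per year or more was 6%, 15% and 34% at true rates of 0.2, 0.5 and 1.0.

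**Step 4: when some flares end follow-up.** Assumed: 60 per arm, true rate 0.80.

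| Assumed share of flares ending follow-up | Mean of subject rates | Total flares / total person-years |
|---|---|---|
| 5% | 0.86 | 0.78 |
| 25% | 1.12 | 0.75 |

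The mean of rates is pushed up because flaring subjects get short denominators. The pooled rate is itself slightly low here, since subjects at higher risk leave earlier.

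**The case against.** Much of the case on the other side stands.

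- **No test or decision depends on these endpoints.** The trial stopped for futility, and section 10 discloses that comparisons were dropped. Only reported estimates are affected.
- **Very short follow-up may be uncommon.** The sixth interim analysis was triggered once 200 subjects had had the opportunity to complete week 24. With about 320 planned at most, that is at least 200/320 = 62.5% of those enrolled. Very short exposures arise only among later enrollees and dropouts, whose number is not stated. If few were cut before week 24, the loss is about 5% in variance.
- **Median, quartiles and maximum are also planned**, and they expose skew. This helps only in part: in the simulation the median was 0 at 0.2 and 0.5 flares per year, so it cannot serve as a rate.

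A reader might also infer three stronger claims, which the documents do not support.

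- *That the reduced SAP removed an exposure-weighted model.* Protocol 10.3.2.2 says only that "Bayesian Hierarchical Model/Generalized linear model will be used to evaluate secondary efficacy endpoints", and leaves details to the SAP. A generalized linear model could have carried an exposure offset, but none is stated for flares.
- *That response-adaptive randomization makes arm differences reflect follow-up length.* Allocation shifts only among the active doses, with placebo held at 25%. A rate already divides by exposure, so under a constant flare risk unequal follow-up changes precision and not the expected rate. If risk varies over time, the pooled rate depends on follow-up too.
- *That the planned means are biased upward.* This needs flare-triggered loss of follow-up. Protocol 8.1 lists disease flare among reasons for removal from investigational product or procedural assessments, so the route exists. But 8.2.1 does not list it as a reason for leaving the study, and subjects off product are encouraged to keep their monthly visits. The 5% and 25% in the working are illustrations.

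**Conclusion.** The point holds as one about choice of summary. On the natural reading, the SAP reports unweighted statistics of subject-level flare rates with no minimum exposure and no person-time rate, in a trial whose follow-up was cut unequally. The 12.6 to 1.0 contrast is plain arithmetic. The cost in precision rests on assumed truncation and flare rates. A variance ratio of about 1.1 to 1.7 means a standard error 5% to 30% larger (square roots 1.05 and 1.30), and the loss is close to nothing if nearly all cuts came after week 24. Systematic bias is possible but not shown, because the share of flares that end follow-up is not in the documents. The change is worth making because the better summary uses data already collected and needs no treatment comparison.

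**What to change.** In Table 9-2, for each of the three flare endpoints and each randomized arm, add:

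- total flares;
- total person-years;
- flares per person-year with a 95% CI that allows for variation between subjects (negative binomial, or Poisson with robust variance, with log exposure as offset).

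Name this as the main summary and keep the planned subject-level descriptive statistics as supportive. A single-arm rate with its interval is still descriptive, so it fits the decision in section 10 to drop comparisons. State in one line how a subject with no post-baseline flare assessment is handled, since the exposure definition gives that subject little or no denominator. Also state whether subjects cut short on 28 February 2023 contribute their follow-up to that date, because section 8.3 is written for visit-level data.

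The cost is one more set of summary rows per flare endpoint and a simple model for the interval. No new data are needed.

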5.7 Patient-reported Outcome (PRO) Assessments

Medical Outcome Short Form-36 Questionnaire Version 2 (SF36v2)

The SF-36v2 (acute version) Health Survey ([Ware et al, 2000](#)) contains 36 items and is a revised version of the SF-36 Health Survey. The SF-36v2 acute version is a patient-reported generic measure of health status. This survey yields assessments of 8 domains of health-related quality of life: 1) limitations in physical activities because of health problems; 2) limitations in social activities because of physical or emotional problems; 3) limitations in usual role activities because of physical health problems; 4) bodily pain; 5) general mental health (psychological distress and well-being); 6) limitations in usual role activities because of emotional problems; 7) vitality (energy and fatigue); and 8) general health perceptions. The scores from the 8 domains will be evaluated independently and aggregated into 2 norm-based summary component measures of physical and mental

health. The recall period is the past 7 days. The scoring of SF-36v2 will be processed by QualityMetric's PRO CoRE Software.

Patient-Reported Outcome Measurement Information System Fatigue Short Form

7a Instrument (PROMIS Fatigue SF 7A v1.0)

The PROMIS Fatigue Short Form 7a is a 7-item instrument originally constructed by the PROMIS Fatigue team to represent the range of the fatigue trait (PROMIS Fatigue Scoring Manual). It assesses the experience of fatigue as well as its impact on physical, mental and social activities. Both psychometric properties and clinical input were used in the development of the short form from the PROMIS item bank. Estimates of responsiveness and minimally important differences have been reported for the 4 item PROMIS Fatigue instrument in SLE patients ([Katz et al, 2019](#)). The PROMIS Fatigue has also been able to differentiate disease activity in other rheumatologic diseases. ([Wohlfahrt et al, 2019](#)). Details of the scoring algorithm are described in [Appendix C](#).

LupusQoL

The LupusQoL is a SLE-specific health-related quality of life instrument (Jolly et al, 2010; [McElhone et al, 2007](#)) for use in adults. The LupusQoL consists of 8 domains: physical health (8 items), pain (3 items), planning (3 items), intimate relationships (2 items), burden to others (3 items), emotional health (6 items), body image (5 items), and fatigue (4 items). The final instrument has demonstrated good internal reliability (Cronbach's 0.88 to 0.95), good test-retest reliability (r 0.72 to 0.93), good concurrent validity with the comparable domains of the SF-36 (r 0.71 to 0.79) and good discriminant validity for different levels of disease activity, measured by BILAG index, and damage (Systemic Lupus International Collaborating Clinics/ACR damage index) but not for all domains. The instrument also has acceptable ceiling effects and minimal floor effects.

Details of the scoring algorithm are described in [Appendix C](#).

Patient Global Assessment (PtGA)

The patient global assessment of disease activity (PtGA) typically assesses disease activity on a 10 cm numeric rating scale (NRS; 0 to 10 cm) or 0-100 response. The scale for the assessment ranges from "very well" (0) to "very poor" (10) ([Furie et al, 2009](#)). The validity of the PtGA in SLE has been established ([Khraishi et al, 2014](#); [Liang et al, 1989](#)). The PtGA scale has a 7-day recall.

6. Analysis Sets

